10.4.2 Statistical hypothesis, model, and method of analysis

In this single-arm trial, the primary objective is to estimate the CBR. Therefore, no statistical hypothesis or model is underlying the analysis.

The CBR (best overall response of CR or PR or SD or NCRNPD) as well as individual response categories (CR, PR, SD, PD, NCRNPD or unknown) will be summarized using frequency tables together with their associated two-sided exact 95% confidence intervals (Clopper-Pearson method). The Full Analysis Set will be used for the primary efficacy analysis.

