10.8 Sample size calculation

Sample size assumptions in this study for postmenopausal patients without prior treatment for advanced disease are based on the data from the CLEE011X2107 study (Juric, poster presented at ASCO 2016), which enrolled a similar patient population.

Regarding patients in later than first lines and pretreated premenopausal patients, assumptions are based on Cristofanilli et al 2016 - PALOMA-3 final analysis.

It is expected that the CBR (based on local assessment) by week 24 is in a range as reported for the CLEE011X2107 study for the ribociclib + letrozole group (CBR = 79%, 95% confidence interval [59% to 92%]).

Using the lower limit of the CI (59%) as a pessimistic estimate for the CBR by week 24, a sample size of 500 produces a two-sided 95% confidence interval with a width equal to 8.6 percentage points (the associated 95% CI is [54.7% to 63.3%]). When using the same CBR as observed (CBR 79%), a sample size of 500 produces a two-sided 95% confidence interval with a width equal to 7.2 percentage points (the 95% CI is [75.4% to 82.6%]). Using the upper limit of the CI (92%) as an optimistic estimate for the CBR, a sample size of 500 produces a two-sided 95% confidence interval with a width equal to 4.8 percentage points (the 95% CI is 89.6% to 94.4%). Assuming an estimated rate of 70% to be recruited in the subgroup of postmenopausal first line patients resulting in a sample size of 350 patients, the width of the confidence interval will be between 10.4 percentage points (pessimistic scenario) and 5.6 percentage points (optimistic scenario).

Regarding the subgroup of second or further treatment lines and premenopausal patients, assuming an estimated rate of 30% to be recruited, and further based on the data as presented by Cristofanili et al. (CBR 67%, 95% CI [61.3% to 71.5%]), the resulting precision based on 150 patients leads to a width of the resulting 95% confidence interval between 15.6 percentage points (pessimistic scenario) and 14.4 percentage points (optimistic scenario). Thus, a sample size of 500 patients allows estimating the CBR in this patient population with reasonable precision.

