Regarding the subgroup of second or further treatment lines and premenopausal patients, assuming an estimated rate of 30% to be recruited, and further based on the data as presented by Cristofanili et al. (CBR 67%, 95% CI [61.3% to 71.5%]), the resulting precision based on 150 patients leads to a width of the resulting 95% confidence interval between 15.6 percentage points (pessimistic scenario) and 14.4 percentage points (optimistic scenario).

Thus, a sample size of 500 patients allows estimating the CBR in this patient population with reasonable precision.

4 Change to protocol specified analyses

Additionally to protocol specified analyses, the time to and duration of RECIST response was analysed for the full analysis set (FAS).

5 Appendix

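### The sample-size section gives normal-approximation (Wald) interval widths, but the primary analysis uses Clopper-Pearson intervals, which are wider at every planned scenario

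*Protocol*

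**What the plan says.** Protocol 10.8, repeated in SAP section 3, justifies 500 patients by interval width alone.

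- **Total population, n=500.** At a CBR of 59%, "a sample size of 500 produces a two-sided 95% confidence interval with a width equal to 8.6 percentage points", and "the associated 95% CI is [54.7% to 63.3"%]. At 79%, "a sample size of 500 produces a two-sided 95% confidence interval with a width equal to 7.2 percentage points", with limits 75.4% and 82.6%. At 92% the width is 4.8 points, with limits 89.6% and 94.4%.
- **Cohort A, n=350.** At the same pessimistic and optimistic rates (59% and 92%), "the width of the confidence interval will be between 10.4 percentage points (pessimistic scenario) and 5.6 percentage points (optimistic scenario".
- **Cohort B, n=150.** The assumed rates are 61.3% (pessimistic) and 71.5% (optimistic). For the first of these, "the resulting precision based on 150 patients leads to a width of the resulting 95% confidence interval between 15.6 percentage points (pessimistic scenario". For the second, the stated width is 14.4 points.

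The section names no interval method. It concludes that 500 patients give reasonable precision and sets no target width.

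The analysis method is fixed elsewhere. Protocol 10.4.2 says the CBR and the response categories are summarised in frequency tables "together with their associated two-sided exact 95% confidence intervals (Clopper-Pearson method". The protocol summary and SAP 2.5.2 say the same. On the purpose of the analysis, Protocol 10.4.2 says: "Therefore, no statistical hypothesis or model is underlying the analysis".

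**The concern.** The three printed intervals are exactly symmetric about the assumed rate: 59 ± 4.3, 79 ± 3.6 and 92 ± 2.4. Clopper-Pearson intervals at rates above 50% are not symmetric; they reach further down than up. The symmetry shows that the planning figures came from a different method.

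The plan has no test and, by Protocol 10.9, no power calculation for secondary variables. Interval width is therefore the only quantitative design property it claims. The primary objective covers the total population and cohorts A and B separately, so all seven figures describe primary estimates. Anyone who checks them with the prespecified method will reproduce none of them, and every difference favours the plan.

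**Working it through.** **Inputs.** Assumed rates and sample sizes from Protocol 10.8: 59%, 79% and 92% at n=500; 59% and 92% at n=350 (70% of 500); 61.3% and 71.5% at n=150 (30% of 500). The level is two-sided 95%.

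**Step 1: reproduce the stated figures.** The Wald half-width is h = 1.96 × √(p(1−p)/n). For p=0.59 and n=500, h = 1.96 × √(0.59 × 0.41/500) = 4.31 points. Rounded to 4.3 and doubled, this gives 8.6, with limits 54.7 and 63.3, as printed. Applied to all seven scenarios:

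| n | p | h | 2h, unrounded | 2 × rounded h | Stated |
|---|---|---|---|---|---|
| 500 | 59% | 4.31 | 8.62 | 8.6 | 8.6 |
| 500 | 79% | 3.57 | 7.14 | 7.2 | 7.2 |
| 500 | 92% | 2.38 | 4.76 | 4.8 | 4.8 |
| 350 | 59% | 5.15 | 10.31 | 10.4 | 10.4 |
| 350 | 92% | 2.84 | 5.68 | 5.6 | 5.6 |
| 150 | 61.3% | 7.79 | 15.59 | 15.6 | 15.6 |
| 150 | 71.5% | 7.22 | 14.45 | 14.4 | 14.4 |

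(For n=350 and p=59%, h is 5.153, which rounds to 5.2.) All seven widths and all three printed intervals are reproduced. Wilson, Agresti-Coull, Jeffreys, continuity-corrected Wald and Clopper-Pearson were also tried; none reproduces the full set.

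**Step 2: apply the prespecified method.** With x responders out of n, the Clopper-Pearson limits are the 0.025 quantile of Beta(x, n−x+1) and the 0.975 quantile of Beta(x+1, n−x). Where np is not a whole number, both neighbouring counts are shown.

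| n | p | x | Clopper-Pearson limits (%) | Width | Stated | Difference |
|---|---|---|---|---|---|---|
| 500 | 59% | 295 | 54.55 to 63.35 | 8.80 | 8.6 | +0.20 |
| 500 | 79% | 395 | 75.16 to 82.49 | 7.33 | 7.2 | +0.13 |
| 500 | 92% | 460 | 89.27 to 94.22 | 4.96 | 4.8 | +0.16 |
| 350 | 59% | 206 | 53.50 to 64.06 | 10.56 | 10.4 | +0.16 |
| 350 | 59% | 207 | 53.79 to 64.34 | 10.55 | 10.4 | +0.15 |
| 350 | 92% | 322 | 88.65 to 94.62 | 5.97 | 5.6 | +0.37 |
| 150 | 61.3% | 91 | 52.37 to 68.53 | 16.17 | 15.6 | +0.57 |
| 150 | 61.3% | 92 | 53.05 to 69.16 | 16.12 | 15.6 | +0.52 |
| 150 | 71.5% | 107 | 63.39 to 78.41 | 15.02 | 14.4 | +0.62 |
| 150 | 71.5% | 108 | 64.09 to 79.02 | 14.92 | 14.4 | +0.52 |

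Every stated width is below the exact one. The largest relative gap is 5.97/5.6 − 1 = 6.7%.

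**Step 3: separate method from rounding.** Against the unrounded Wald width, the exact width is larger by between 2.1% (8.80/8.62, n=500 at 59%) and 5.1% (5.97/5.68, n=350 at 92%). The rest of the 6.7% comes from rounding the half-width before doubling. The same rounding pushes 10.4 and 7.2 slightly above their Wald values (10.31 and 7.14), which hides part of the gap there.

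**Step 4: the gap expressed in patients.** To bring the Clopper-Pearson width down to the stated width at the same rate would take 524, 518 and 533 patients instead of 500; 361 and 396 instead of 350; and 160 and 163 instead of 150. This is only a way to gauge the mismatch.

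**The case against.** The strongest reply is that nothing turns on the difference. The plan sets no target width, only a judgement of reasonable precision, and a reader content with 8.6 or 15.6 points would hardly object to 8.8 or 16.1. The plan's own scenarios at n=500 range from 4.8 to 8.6 points, far more than the method effect. No test, power figure or interim rule uses these widths. Enrollment was complete by Amendment 4, and the reported intervals will be Clopper-Pearson whatever Protocol 10.8 says. All of this stands and sets the priority low.

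A second reply is that the width finally obtained depends on the observed CBR and the actual Full Analysis Set. At 400/500 (80%) the exact width is 7.20, equal to the figure stated for 79%; at 405/500 (81%) it is 7.06. This is also right. The comparison holds at the same assumed rate and n and does not predict that the reported intervals must be wider than those printed.

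A third reply is that Protocol 10.8 never claims its widths are exact, so labelling them would remove the inconsistency. That is a fair alternative, but a label alone would leave 10.4, 5.6 and 7.2 misrounded; unrounded Wald gives 10.3, 5.7 and 7.1.

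None of these replies disputes the arithmetic, and nothing in either document reconciles the two methods.

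**Conclusion.** The concern holds. All seven planned widths are Wald figures, and each is narrower than the prespecified Clopper-Pearson interval at the same rate and sample size: by 0.1 to 0.2 points for the total population, 0.15 to 0.4 for cohort A and 0.5 to 0.6 for cohort B. The method itself accounts for about 2% to 5%; rounding raises the largest gap to about 7%. The result assumes the planned rates, the planned 350/150 split and a Full Analysis Set of 500.

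This is a low-priority correction to the only quantitative basis for the sample size. It does not overturn the conclusion of reasonable precision, call for a different N, or affect any reported estimate.

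**What to change.** In Protocol 10.8 and SAP section 3, name the Clopper-Pearson method and restate the widths:

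- **n=500:** 8.8, 7.3 and 5.0 points, with intervals 54.5% to 63.3% (295/500; unrounded width 8.80), 75.2% to 82.5% and 89.3% to 94.2%.
- **n=350:** 10.6 points (206/350) and 6.0 points.
- **n=150:** 16.1 points (92/150) and 15.0 points (107/150).

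State the counts, because np is not a whole number in three scenarios. If the protocol is not to be amended again, make the change in the SAP and the study report.

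The minimum alternative is one sentence saying the widths are normal approximations while the analysis uses exact intervals, with 10.4, 5.6 and 7.2 corrected to 10.3, 5.7 and 7.1.

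Either is a text edit with no change to N, data collection or analysis. The only cost is that the exact figures look slightly less favourable.

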10.9 Power for analysis of key secondary variables

Not applicable. Power for analysis of secondary variables was not investigated.

11 Ethical considerations and administrative procedures

11.1 Regulatory and ethical compliance

This clinical study was designed, shall be implemented and reported in accordance with the ICH Harmonized Tripartite Guidelines for Good Clinical Practice, with applicable local regulations (including European Directive 2001/20/EC and US Code of Federal Regulations Title 21), and with the ethical principles laid down in the Declaration of Helsinki.

11.2 Responsibilities of the investigator and IRB/IEC/REB

The protocol and the proposed informed consent form must be reviewed and approved by a properly constituted Institutional Review Board/Independent Ethics Committee/Research Ethics Board (IRB/IEC/REB) before study start. Prior to study start, the investigator is required to sign a protocol signature page confirming his/her agreement to conduct the study in accordance with these documents and all of the instructions and procedures found in this protocol and to give access to all relevant data and records to Novartis monitors, auditors, Novartis Clinical Quality Assurance representatives, designated agents of Novartis, IRBs/IECs/REBs and regulatory authorities as required.

11.3 Informed consent procedures

Eligible patients may only be included in the study after providing written (witnessed, where required by law or regulation), IRB/IEC/REB-approved informed consent.

Informed consent must be obtained before conducting any study-specific procedures (i.e. all of the procedures described in the protocol). The process of obtaining informed consent should be documented in the patient source documents. The date when a subject's Informed Consent was actually obtained will be captured in their CRFs.

Novartis will provide to investigators, in a separate document, a proposed informed consent form (ICF) that is considered appropriate for this study and complies with the ICH GCP guideline and regulatory requirements. Any changes to this ICF suggested by the investigator must be agreed to by Novartis before submission to the IRB/IEC/REB, and a copy of the approved version must be provided to the Novartis monitor after IRB/IEC/REB approval.

Women of child bearing potential should be informed that taking the study medication may involve unknown risks to the fetus if pregnancy were to occur during the study and agree that in order to participate in the study they must adhere to the contraception requirement for the duration of the study. If there is any question that the patient will not reliably comply, they should not be entered in the study.

Additional consent form

Sub-studies and studies with an optional Exploratory Biomarker component will have a separate consent form covering those studies. This informed consent form will be submitted for ethical approval together with the Study Protocol and the main informed consent form of the Study. If a subject opts not to participate in the optional assessments, this in no way affects the subject's ability to participate in the main research study.

11.4 Discontinuation of the study

Novartis reserves the right to discontinue this study under the conditions specified in the clinical study agreement. Specific conditions for terminating the study are outlined in Section 4.4.

11.5 Publication of study protocol and results

Novartis assures that the key design elements of this protocol will be posted in a publicly accessible database such as clinicaltrials.gov. In addition, upon study completion and finalization of the study report the results of this study will be either submitted for publication and/or posted in a publicly accessible database of clinical study results.

11.6 Study documentation, record keeping and retention of documents

Each participating site will maintain appropriate medical and research records for this trial, in compliance with Section 4.9 of the ICH E6 GCP, and regulatory and institutional requirements for the protection of confidentiality of subjects. As part of participating in a Novartis-sponsored study, each site will permit authorized representatives of the sponsor(s) and regulatory agencies to examine (and when required by applicable law, to copy) clinical records for the purposes of quality assurance reviews, audits and evaluation of the study safety and progress.

Source data are all information, original records of clinical findings, observations, or other activities in a clinical trial necessary for the reconstruction and evaluation of the trial. Examples of these original documents and data records include, but are not limited to, hospital records, clinical and office charts, laboratory notes, memoranda, subjects' diaries

or evaluation checklists, pharmacy dispensing records, recorded data from automated instruments, copies or transcriptions certified after verification as being accurate and complete, microfiches, photographic negatives, microfilm or magnetic media, x-rays, and subject files and records kept at the pharmacy, at the laboratories, and medico-technical departments involved in the clinical trial.

Data collection is the responsibility of the clinical trial staff at the site under the supervision of the site Principal Investigator. The study case report form (CRF) is the primary data collection instrument for the study. The investigator should ensure the accuracy, completeness, legibility, and timeliness of the data reported in the CRFs and all other required reports. Data reported on the CRF, that are derived from source documents, should be consistent with the source documents or the discrepancies should be explained. All data requested on the CRF must be recorded. Any missing data must be explained. Any change or correction to a paper CRF should be dated, initialed, and explained (if necessary) and should not obscure the original entry. For electronic CRFs an audit trail will be maintained by the system. The investigator should retain records of the changes and corrections to paper CRFs.

The investigator/institution should maintain the trial documents as specified in Essential Documents for the Conduct of a Clinical Trial (ICH E6 Section 8) and as required by applicable regulations and/or guidelines. The investigator/institution should take measures to prevent accidental or premature destruction of these documents.

Essential documents (written and electronic) should be retained for a period of not less than fifteen (15) years from the completion of the Clinical Trial unless Sponsor provides written permission to dispose of them or, requires their retention for an additional period of time because of applicable laws, regulations and/or guidelines.

11.7 Confidentiality of study documents and patient records

The investigator must ensure pseudonymity of the patients; patients must not be identified by names in any documents submitted to Novartis. Signed informed consent forms and patient enrollment log must be kept strictly confidential to enable patient identification at the site.

11.8 Audits and inspections

Source data/documents must be available to inspections by Novartis or designee or Health Authorities.

12 Protocol adherence

Investigators ascertain they will apply due diligence to avoid protocol deviations. Under no circumstances should the investigator contact Novartis or its agents, if any, monitoring the study to request approval of a protocol deviation, as no authorized deviations are permitted. If the investigator feels a protocol deviation would improve the conduct of the study this must be considered a protocol amendment, and unless such an amendment is agreed upon by Novartis and approved by the IRB/IEC/REB it cannot be implemented. All significant protocol deviations will be recorded and reported in the CSR.

14.1 Appendix 1 – Concomitant Medications

In general, the use of any concomitant medication deemed necessary for the care of the patient is permitted in this study, except as specifically prohibited below. Combination administration of study drugs could result in drug-drug interactions (DDI) that could potentially lead to reduced activity or enhanced toxicity of the concomitant medication and/or ribociclib.

The following lists are not comprehensive and are only meant to be used as a guide. The lists are based on Oncology Clinical Pharmacology guidance, Drug-Drug Interaction and Co-Medication Considerations (v07, release date: Jan 2018), which was compiled from the Indiana University School of Medicine's P450 Drug Interaction Table (<http://medicine.iupui.edu/clinpharm/ddis/main-table/>) and supplemented with the FDA Draft Guidance for Industry, Drug Interaction Studies – Study Design, Data Analysis, and Implications for Dosing and Labeling (February 2012) (<http://www.fda.gov/downloads/drugs/guidancecomplianceregulatoryinformation/guidances/ucm292362.pdf>), and the University of Washington's Drug Interaction Database (<http://www.druginteractioninfo.org/>). For current lists of medications that may cause QT prolongation and/or torsades de pointes (TdP), refer to the CredibleMeds® website (www.qtdrugs.org/). Please contact the medical monitor with any questions.

Table 14-1 List of prohibited medications during study drug treatment

Category	Drug Name
Strong CYP3A4/5 inhibitors	Atazanavir/ritonavir, boceprevir, clarithromycin, cobicistat, conivaptan, danoprevir/ritonavir, darunavir/ritonavir, elvitegravir/ritonavir, grapefruit juice, idelalisib, indinavir, indinavir/ritonavir, itraconazole, ketoconazole, lopinavir/ritonavir, mibefradil, nefazodone, neflifavir, ombitasvir/paritaprevir/dasabuvir/ritonavir (VIEKIRA PAK), posaconazole, ritonavir, saquinavir/ritonavir, telaprevir, telithromycin, tipranavir/ritonavir, troleandomycin, voriconazole
Strong CYP3A4/5 inducers	Avasimibe^{2,3}, carbamazepine, enzalutamide, lumacaftor, mitotane, phenobarbital, phenytoin³, rifabutin, rifampin (rifampicin)³, St. John's wort (hypericum perforatum)^{2,3}
CYP3A4/5 substrates with NTI ¹	Alfentanil, astemizole, cisapride, cyclosporine, diergotamine, dihydroergotamine, ergotamine, fentanyl, lomitapide⁵, lovastatin, nicardipine, nisoldipine, pimozide, quinidine, simvastatin, sirolimus, tacrolimus
Medications with a known risk for QT prolongation ⁴	Amiodarone, anagrelide, arsenic trioxide, astemizole, azithromycin, bepridil, chloroquine, cocaine, chlorpromazine, cilostazol, ciprofloxacin, cisapride, citalopram, clarithromycin, disopyramide, dofetilide, domperidone, donepezil, dronedarone, droperidol, erythromycin, escitalopram, flecainide, fluconazole, gatifloxacin, grepafloxacin, halofantrine, haloperidol, ibutilide, levofloxacin, levomepromazine, levosulpiride, levomethadyl, mesoridazine, methadone, moxifloxacin, ondansetron, oxaliplatin, papaverine HCl (intracoronary), pentamidine, pimozide, probucol, procainamide, propofol, quinidiner, roxithromycin, sevoflurane, sotalol, sparfloxacin, sulpiride, sultopride, terlipressin, terodilene, terfenadine, thioridazine, vandetanib
Herbal preparations/medications	Herbal preparations/medications known as strong inducers or inhibitors of CYP3A4/5 or those with a known risk of QT prolongation are prohibited throughout the study. These herbal medications include, but are not limited to: St. John's wort, Kava, ephedra (ma huang), gingko biloba, dehydroepiandrosterone (DHEA), yohimbe, saw palmetto, and ginseng. Patients should stop using these herbal medications 7 days prior to first dose of study drug.

Category	Drug Name
Other investigational and antineoplastic therapies	Other investigational therapies must not be used while the patient is on the study. Anticancer therapy (chemotherapy, biologic or radiation therapy, except for palliative radiotherapy as outlined in the protocol , and surgery) other than the study treatments must not be given while the patient is on the study medication. If such agents are required then the patient must discontinue study drug.

¹ NTI = narrow therapeutic index drugs whose exposure-response indicates that increases in their exposure levels by the concomitant use of potent inhibitors may lead to serious safety concerns (e.g., Torsades de Pointes) or drugs which have <2-fold difference in the minimum toxic concentrations and minimum effective concentrations in the blood...

² Herbal product

³ P-gp inducer

⁴ Source: www.qtdrugs.org (as of Apr 7, 2015)

⁵ Drug has warning for risk of hepatotoxicity.

As far as possible, avoid co-administration of QT prolonging drugs or any other drugs with the potential to increase the risk of drug-related QT prolongation (e.g., via a potential DDI that increases the exposure of ribociclib or the exposure of the QT prolonging drug). A definitive list of drugs with a known risk, possible risk, or conditional risk of QT prolongation and/or Torsades de Pointes (TdP) is available online at qtdrugs.org.

Table 14-2 List of medications to be used with caution during study drug treatment

Category	Drug Name
Moderate CYP3A4/5 inhibitors	Aprepitant , amprenavir, asafoetida resin (Ferula asafoetida), cimetidine, crizotinib, diltiazem, faldaprevir , imatinib , isavuconazolef , netupitant, nilotinib, tofisopam, Schisandra sphenanthera (nan wu wei zi), verapamil
Moderate CYP3A4/5 inducers	Bosentan, dabrafenib, efavirenz, etravirine, genistein, iversivirine, lopinavir ⁵ , modafinil, naftilin, telotristat
Sensitive CYP3A4/5 substrates ¹	Alpha-dihydroergocryptine, apixaban, aprepitant, atorvastatin, avanafil, bosutinib, brotizolam, budesonide, buspirone, cobimetinib, darifenacin, dasatinib, ebastine, eletriptan, eplerenone, everolimus, grazoprevir, ibrutinib, isavuconazole, ivabradine, ivacaftor, lumefantrine, luridone, maraviroc, midazolam, perospirone, quetiapine, ridaforolimus, rivaroxaban, sildenafil, simeprevir, ticagrelor, tilidine, tolvaptan, triazolam, ulipristal, vardenafil, venetoclax, viceriviroc, voclosporin
BSEP inhibitors	Alectinib, atorvastatin, bromocriptine, candesartan, clobetasol, clofazimine, dabigatran, dipyridamole, glyburide, grazoprevir, ledipasvir, mifepristone, pioglitazone, reserpine, rifamycin, simeprevir, telmisartan, timodar, troglitazone, valinomycin, velpatasvir
Medications that carry a possible risk for QT prolongation ²	Alfuzosin, apomorphine, aripiprazole, artenimol+piperaquine, asenapine, atazanavir, atomoxetine, bedaquiline, bendamustine, bortezomib, bosutinib, buprenorphine, cabozantinib, capecitabine, ceritinib, clomipramine, crizotinib, clozapine, cyamemazine (cyamepromazine), dabrafenib, dasatinib, degarilix, delamanid, desipramine, dexametomidine, dolasetron, efavirenz, eliglustat, epirubicin, eribulin mesylate, ezogabine (retigabine), famotidine, felbamate, fingolimod, flupentixol, gemifloxacin, granisetron, hydrocodone-ER, iloperidone, imipramine (mepipramine), isradipine, ketanserin, lapatinib, lenvatinib, leuprolide, loperamide, lithium, melperone, midostaurin, mifepristone, mirabegron, mirtazapine, moxipril/HCTZ, necitumumab, nilotinib, norfloxacin, nortriptyline, nusinersen, ofloxacin, olanzapine, osimertinib, oxytocin, paliperidone, palonosetron, panobinostat, pasireotide, pazopanib, perflutren lipid microspheres, perphenazine, pilsicainide, pimavanserin, pipamperone, promethazine, prothipendyl, quetiapine, ranolazine, rilpivirine, risperidone, romidepsin, sertindole, sorafenib, sunitinib, tamoxifen, telavancin, tetrabenazine, tipiracil/trifluridine, tizanidine, tolterodine, toremifene, trimipramine, tropisetron, vardenafil, vemurafenib, venlafaxine, vardenafil, ziprasidone
MATE1/2 substrates ³	Acyclovir, cephalexin, cimetidine, fexofenadine, ganciclovir, glycopyrronium, metformin, pindolol, pilsicainide , ranitidine, topotecan and varencicline
OCT1/2 substrates ⁴	Amantadine, 6-beta-hydroxycortisol, carboplatin, cisplatin, cephalexin, cephradine, ipratropium, lamivudine, linagliptin, metformin, oxyplatin, oxybutynin, phenformin, picoplatin, pilsicainide, pindolol, ranitidine, sorafenib, tropisetron, trospium, umeclidinium, and zidovudine
BCRP substrates	Daunorubicin, dolutegravir , doxorubicin, hematoporphyrin , imatinib, methotrexate, mitoxantrone, pitavastatin, rosuvastatin , irinotecan, ethinyl estradiol, and sulfasalazine, sofosbuvir , tenofovir , topotecan, venetoclax

¹ Sensitive substrates includes drugs whose plasma AUC values have been shown to increase 5-fold or higher when co-administered with a potent inhibitor.

² The list provided is as of January 2018. Check crediblemeds.org/healthcare-providers/drug-list for the most updated list.³ MATE1 and MATE2 share considerable substrate specificity.

⁴ OCT1 and OCT2 share considerable substrate specificity.

⁵ Lopinavir is prohibited when combined with ritonavir (see Table 14-1)

Source: Novartis PK Sciences Memorandum: Drug-Drug Interactions (DDI) and Co-medication Considerations for Novartis Clinical Trials (January 2018), which is compiled from Indiana University "Clinically Relevant" Flockhart Table™, University of Washington Drug Interaction Database, and FDA Drug Development and Drug Interactions: Table of Substrates, Inhibitors and Inducers

14.2 Appendix 2: Guidelines for response, duration of overall response, TTF, TTP, progression-free survival and overall survival (based on RECIST 1.1)

Document type: TA Specific Guideline

Document status: Version 3.1: 29-Nov-2011
Version 3:0: 19-Oct-2009
Version 2:0: 18-Jan-2007
Version 1:0: 13-Dec-2002

Release date: 29-Nov-2011

List of contributors

[figure not shown]
Authors (Version 3.1):

Authors (Version 3):

Authors (Version 2):

Authors (Version 1):

Glossary

CR	Complete response
CRF	Case Report Form
CSR	Clinical Study Report
CT	Computed tomography
DFS	Disease free survival
eCRF	Electronic Case Report Form
FFPV	First patient first visit
GBM	Glioblastoma multiforme
MRI	Magnetic resonance imaging
LPLV	Last patient last visit
OS	Overall survival
PD	Progressive disease
PFS	Progression free survival
PR	Partial response
RAP	Reporting and Analytic Plan
RECIST	Response Evaluation Criteria in Solid Tumors
SD	Stable disease
SOD	Sum of Diameter
TTF	Time to treatment failure
TPR	Time to progression
UNK	Unknown

1 Introduction

The purpose of this document is to provide the working definitions and rules necessary for a consistent and efficient analysis of efficacy for oncology studies in solid tumors. This document is based on the RECIST criteria for tumor responses ([Therasse et al 2000](#)) and the revised RECIST 1.1 guidelines ([Eisenhauer et al 2009](#)).

The efficacy assessments described in [Section 2](#) and the definition of best response in [Section 3.1](#) are based on the RECIST 1.1 criteria but also give more detailed instructions and rules for determination of best response. [Section 3.2](#) is summarizing the “time to event” variables and rules which are mainly derived from internal discussions and regulatory consultations, as the RECIST criteria do not define these variables in detail. [Section 4](#) of this guideline describes data handling and programming rules. This section is to be referred to in the RAP (Reporting and Analysis Plan) to provide further details needed for programming.

2 Efficacy assessments

Tumor evaluations are made based on RECIST criteria ([Therasse et al 2000](#)), New Guidelines to Evaluate the Response to Treatment in Solid Tumors, Journal of National Cancer Institute, Vol. 92; 205-16 and revised RECIST guidelines (version 1.1) ([Eisenhauer et al 2009](#)) European Journal of Cancer; 45:228-247.

